- The difference between treatments in the change in subject reported Quality of Life (QoL) during the 12-week treatment period. The Health related Quality of Life (HRQoL) will be assessed using the EQ-5D and CWIS validated instruments. Study subjects will complete both instruments at the Randomization Study Visit 1 and at the End of Treatment period. The change in continuous measures of the EQ-5D and CWIS instruments (including Time Trade-off (TTO) index, EQ-VAS, and domain averages) between the randomization Study Visit 1 and End of Treatment period will be derived as follows using the relevant variable:

(Value at End of Treatment period – Value at Randomization Study Visit 1)

Exploratory Endpoints

The exploratory endpoints are as follows:

- Assessment of change in target ulcer progression parameters over the 12-weeks and comparison between treatments including: Estimation of the types of tissue present on the target ulcer, Presence of Infection/Clinical signs of infection, Condition of peri-wound skin, Need for administration of antibiotics and additional interventions, dressing wear time, pain on removal of dressing and at initiation of, and during, therapy.

The subject's target ulcer will be assessed by the Investigator at each study visit. Where possible this assessment will be made using a modified Bates-Jensen wound assessment tool, this will include information concerning presence of Undermining, Necrotic Tissue Type and Amount, Exudate Type and Amount, Granulation Tissue and Epithelialization. Otherwise the Investigator's assessment against a custom descriptive scale will be used.

Condition of peri-wound skin will be assessed by the Investigator against a custom 7-category descriptive scale: Normal, Erythematous, Edematous, Eczematous, Excoriated, Macerated and Indurated. Presence of each skin type will be recorded.

Assessment of the presence of infection and clinical signs of infection will be undertaken by the Investigator.

Presence of Undermining, Necrotic Tissue Type and Amount, Exudate Type and Amount, Granulation Tissue and Epithelialization will be assessed using the modified Bates Jensen wound assessment tool.

Pain associated with removal of dressing, and at initiation of, and during, therapy will be assessed using the Pain VAS scale.

The need for administration of antibiotics and additional interventions in the opinion of the Investigator will be recorded.

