10.3 EFFICACY ANALYSIS

10.3.1 Primary Efficacy

The primary endpoint of the study is the percentage change in target ulcer area over the 12-week treatment period and will be analyzed as follows. An initial linear regression model will contain covariates for treatment, center, wound type, baseline (defined as Study Visit 1) target ulcer area and duration of target ulcer. For purposes of the primary analysis, any centers with less than 10 subjects will be pooled. A forward selection procedure will be used for the addition of other baseline covariates with an F-value to attain a significance level of 0.1. Further baseline covariates to be assessed as part of this procedure include: subject age, body mass index, baseline ulcer depth, ABI and baseline level of exudate. The resulting primary analysis presented will correspond to the final model from the forward selection procedure. The results for the initial model will also be presented. For each of the effects in the initial and final model, the p-value, parameter estimate and corresponding 95.4% confidence interval will be presented.

Secondary subgroup analyses may be conducted as a result of the covariate analyses. Additionally, treatment will be fitted on its own in a further linear regression model. The potential for interactions, particularly treatment by center interactions will be examined by fitting the required interaction terms in addition to those effects in the final linear regression model from the forward selection procedure.

Non-inferiority will be concluded in each case if the upper bound of the 95.4% confidence interval for the parameter estimate relating to treatment covariate (coded as tNPWT – PICO) is less than ($<$) 12.5 which relates to the desired one-sided test at the 2.5% significance level after adjusting for the interim analysis.

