18.5 EQ-5D

The EQ-5D-5L still consists of 2 pages – the EQ-5D-5L descriptive system and the EQ visual Analogue scale (EQ VAS). The descriptive system comprises the same 5 dimensions as the EQ-5D-5D-3L (mobility, self-care, usual activities, pain/discomfort, anxiety/depression). However, each dimension now has 5 levels: no problems, slight problems, moderate problems, severe problems, and extreme problems.

[figure not shown]
The respondent is asked to indicate his/her health state by ticking (or placing a cross) in the box against the most appropriate statement in each of the 5 dimensions. This decision results in a 1-digit number expressing the level selected for that dimension. The digits for 5 dimensions can be combined in a 5-digit number describing the respondent’s health state.

Under each heading, please tick the ONE box that best describes your health TODAY.

- MOBILITY**
- I have no problems in walking about
 - I have slight problems in walking about
 - I have moderate problems in walking about
 - I have severe problems in walking about
 - I am unable to walk about
- SELF-CARE**
- I have no problems washing or dressing myself
 - I have slight problems washing or dressing myself
 - I have moderate problems washing or dressing myself
 - I have severe problems washing or dressing myself
 - I am unable to wash or dress myself
- USUAL ACTIVITIES** (e.g. work, study, housework, family or leisure activities)
- I have no problems doing my usual activities
 - I have slight problems doing my usual activities
 - I have moderate problems doing my usual activities
 - I have severe problems doing my usual activities
 - I am unable to do my usual activities
- PAIN / DISCOMFORT**
- I have no pain or discomfort
 - I have slight pain or discomfort
 - I have moderate pain or discomfort
 - I have severe pain or discomfort
 - I have extreme pain or discomfort
- ANXIETY / DEPRESSION**
- I am not anxious or depressed
 - I am slightly anxious or depressed
 - I am moderately anxious or depressed
 - I am severely anxious or depressed
 - I am extremely anxious or depressed

- We would like to know how good or bad your health is TODAY.
- This scale is numbered from 0 to 100.
- 100 means the best health you can imagine.
0 means the worst health you can imagine.
- Mark an X on the scale to indicate how your health is TODAY.
- Now, please write the number you marked on the scale in the box below.

YOUR HEALTH TODAY =

CONFIDENTIAL DOCUMENT

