Study subjects will complete both instruments at the Randomization Study Visit 1 and at the End of Treatment period. Scoring/coding of responses, and the change in continuous measures of the EQ-5D and CWIS instruments (including Time Trade-off (TTO) index, EQ-VAS, and domain averages) between the Randomization/Study Visit 1 and End of Treatment will be calculated according to the suppliers validated instructions.

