- Ulcer Closed/Ready for surgical closure =Yes at last attended Study Visit i, Ulcer Closed=missing at Follow up assessment (Visit 14). Confirmed Closure = missing
- Ulcer Closed/Ready for surgical closure =No at last attended Study Visit i. Confirmed Closure = No

In cases where the ulcer closure status is missing at a Study Visit, the Last Observation Carried Forward (LOCF) method will be used.

21. The derivation for whether confirmed ulcer closure was achieved will be repeated to form two further separate variables, with the exceptions below:

- i. In cases where subjects had missing data over the confirmatory target ulcer closure period (1 week follow-up) and it is unknown whether the closure is confirmed, these will be imputed as: Confirmed Closure=No. All remaining scenarios will be derived as described in the previous derived variable.
- ii. In cases where subjects withdraw from the study prior to the end of the 12-week treatment period (except in cases where the ulcer has closed), the following will be imputed: Confirmed Closure=Yes. All remaining scenarios will be derived as described in the previous derived variable.

22. The components of the CWIS will be derived as follows at baseline and end of treatment.

a) Physical symptoms and daily living

Each individual response will be coded by the following formulae:

Document Number:	1004313	Document Part:	000
Document Version:	06	Document Status:	Released

ST:

9

7

5

Reference:

CE/052/PIC

Customer Code:

0

5

Not at all/Not applicable – 5

Seldom/Slightly – 4

Sometimes/Moderately – 3

Frequently/Quite a bit – 2

Always/Very – 1

An overall score for this domain will then be calculated as the sum of the 24 individual values (12 individual values each for experience and stress related measures).

The overall score will then be transformed onto a scale of 0-100 using the following formula:

$$[(\text{Overall actual score (sum of 24 individual scores)} - \text{minimum possible score}) / \text{range of possible scores}] * 100$$

If all 24 questions are completed, the minimum value =24 and the range of scores = (120 - 24) = 96

b) Social Life

Each individual response will be coded by the following formulae:

Not at all/Not applicable – 5

Seldom/Slightly – 4

Sometimes/Moderately – 3

Frequently/Quite a bit – 2

Always/Very – 1

An overall score for this domain will then be calculated as the sum of the 14 individual values (7 individual values each for experience and stress related measures).

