The overall score will then be transformed onto a scale of 0-100 using the following formula:

$$[(\text{Overall actual score (sum of 14 individual scores)} - \text{minimum possible score}) / \text{range of possible scores}] * 100$$

If all 14 questions are completed, the minimum value =14 and the range of scores = (70 - 14) = 56

c) Well-being

Each individual response will be coded by the following formulae:

Document Number: 1004313

Document Part: 000

Document Version: 06

Document Status: Released

Strictly disagree – 5

Disagree – 4

Not sure – 3

Agree – 2

Strongly agree – 1

NOTE: 'I am confident that the wound(s) I have will heal' will be coded in reverse (strictly disagree-1, disagree-2, not sure-3, agree-4, strongly agree-5).

An overall score will be calculated as the average of the 7 individual values for the wellbeing domain.

The overall score will then be transformed onto a scale of 0-100 using the following formula:

$$\left[\frac{\text{Overall actual score (sum of 7 individual scores)} - \text{minimum possible score}}{\text{range of possible score}} \right] * 100$$

If all 7 questions are completed, the minimum value =7 and the range of scores = (35 - 7) = 28

23. The change in each of the CWIS scores (Wellbeing, Physical symptoms and daily living, Social life, Overall HRQoL and Patient Satisfaction with overall HRQoL) between baseline and end of treatment period will be derived separately as:

$$\text{Score at Baseline (Randomization)} - \text{Score at End of Treatment}$$

24. The responses to the individual EQ-5D-5L domains will be coded as detailed in the references (§6) for the Mobility, Self-care, Usual Activities, Pain/Discomfort and Anxiety/Depression domains. The individual domain responses on a scale of 1-5 will be combined in the previously defined order to form a 5-digit number in the form XXXXX (where X is 1-5) describing the respondent's health state.

25. The change in EQ-5D VAS between baseline and end of treatment period will be derived as:

$$\text{Score at Baseline (Randomization)} - \text{Score at End of Treatment}$$

26. The duration of dressing wear (dressing level) for each individual dressing will be derived as follows per assessment:

Document Number:	1004313	Document Part:	000
Document Version:	06	Document Status:	Released

ST:

9 7 5

Reference:

CE/052/PIC

Customer Code:

0 5

If no unscheduled visit takes place between consecutive assessments:

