In addition, a sensitivity analysis will be performed to ensure that the efficacy findings are not reliant on assumptions made in either the analysis or derivations. For purposes of the sensitivity analysis, the time to confirmed closure for those subjects discontinuing the treatment period prematurely, will be censored at the maximum possible duration of treatment under the study protocol (84 days), rather than time of actual discontinuation. Lastly, the two sensitivity analyses defined in the proportion of subjects achieving confirmed closure analysis will be repeated for the time to confirmed closure, in these cases the censoring flag may be modified as detailed previously, but the time in days will remain unchanged.

Change in subject reported Quality of Life (QoL)

The instruments used to assess subject reported Quality of Life will be the Cardiff Wound Impact Schedule (CWIS) and the EQ-5D. All analyses relating to Quality of Life assessments will be performed using the Full Analysis Set.

Cardiff Wound Impact Schedule

The parameters for each of the domains of the CWIS questionnaire (Wellbeing, Physical symptoms and daily living, Social life) in addition to Overall HRQoL and Patient Satisfaction with overall HRQoL at baseline and end of treatment will be summarized using frequency distributions which will detail the number and percentage of subjects which fall into each category. The change in the CWIS score for each of the domains between baseline and end of treatment will be summarized.

A two sample t-test will be used to test for a difference in the mean change in CWIS score between treatments for each of the domains separately. 95% confidence intervals will also be presented. If the assumptions of the t-test are violated, the Wilcoxon rank sum test will be used instead with Hodges-Lehmann estimates of the median difference and 95% confidence interval reported.

As a sensitivity analysis, the above analysis will be repeated with any missing values coded using LOCF.

EQ-5D

Subject responses to the EQ VAS scale and derived Time Trade-off (TTO) indexes and domain averages at each assessment are continuous variables and will be summarized.

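### Quality-of-life change is subtracted in opposite directions in the SAP and the protocol, and the two documents name different tests for it

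*SAP*

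**What the plan says.** **Change.** Protocol 9.4 defines change in the continuous EQ-5D and CWIS measures, expressly including the TTO index, EQ VAS and domain averages, as "Value at End of Treatment period – Value at Randomization Study Visit 1". SAP 4.3 reverses this. Item 23 derives the CWIS change as the baseline score minus the end-of-treatment score. Item 25, which opens "The change in EQ-5D VAS between baseline and end of treatment period will be derived as", uses the same reversed order. SAP 2.3.2 says that scoring and change in these measures "will be calculated according to the suppliers validated instructions" and gives no formula. SAP 4.3 has no item for the TTO index change, although SAP 4.10 tests it.

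**Scale direction.** The EQ VAS page in Protocol 18.5 states that "100 means the best health you can imagine". The CWIS symptom and social-life items in SAP 4.3 item 22 give the best answer the highest code: "Not at all/Not applicable – 5".

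**Arm order.** It is stated for the primary model only, in Protocol 10.3.1: "parameter estimate relating to treatment covariate (coded as tNPWT – PICO" (SAP 4.9 matches, with the comparator named as ActiV.A.C.).

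**Test.** Protocol 10.3.2 specifies a Wilcoxon rank-sum test stratified by wound strata for change in EQ VAS, repeated for the TTO index and domain averages. SAP 4.10 specifies for CWIS: "A two sample t-test will be used to test for a difference in the mean change in CWIS score between treatments for each" domain. It uses the same test for EQ VAS and the TTO index. Its fallback is an unstratified Wilcoxon test with a Hodges-Lehmann estimate. Randomization is stratified by wound type and size into four strata (Protocol 8.1, SAP 3.2). Neither document puts the baseline quality-of-life score in the analysis, although both instruments are completed at Study Visit 1.

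**The concern.** Health-related quality of life is a stated secondary objective. On scales where higher is better, one subtraction order shows improvement as positive and the other as negative. A team programming from SAP 4.3 would report mean changes, treatment differences and confidence intervals with the opposite sign to the protocol's definition of the endpoint.

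The test is a separate matter. A reader with both documents finds two prespecified first-line analyses of one endpoint, one rank-based and stratified, the other mean-based and unstratified. They can lead to different conclusions from the same data, which invites the question of which was planned. The SAP's version, fallback included, also drops the factors on which subjects were randomized.

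**Working it through.** The documents give no effect size, SD or baseline-to-end correlation for quality of life, and no power figure for it, so there is no stated figure to reproduce. The sample size of 128 (64 per arm) belongs to the primary endpoint and is used here for illustration only.

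**1. Sign.** Take a subject whose EQ VAS goes from 60 to 75 (illustrative).

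| Rule | Calculation | Change |
|---|---|---|
| Protocol 9.4 | 75 - 60 | +15 |
| SAP 4.3 item 25 | 60 - 75 | -15 |

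If PICO subjects gain 15 on average and tNPWT subjects gain 5, the difference depends on both conventions:

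| Arm order | Protocol rule | SAP rule |
|---|---|---|
| PICO - tNPWT | 15 - 5 = +10 | -15 - (-5) = -10 |
| tNPWT - PICO | -10 | +10 |

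Reversing the subtraction multiplies the test statistic by -1 and leaves the two-sided p-value alone. In one simulated data set the arm means were +12.4 and +1.8 under the protocol rule and -12.4 and -1.8 under the SAP rule, with t = 3.08 and -3.08 and p = 0.0026 both ways.

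**2. Do the two tests differ in practice?** Simulation of 128 subjects in balanced arms. Assumptions: four strata of 44, 44, 20 and 20 (the 100:46 VLU:DFU minima scaled to 128 and halved by size), with strata explaining 0% or 15% of the variance. The stratified Wilcoxon is the van Elteren test with weights 1/(n+1). Entries are the share of trials in which exactly one test is significant at 5%.

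| Comparison | No effect | 0.35 SD | 0.5 SD |
|---|---|---|---|
| SAP t-test against protocol test, normal scores | about 2.5% | about 9% | about 5-7% |
| SAP fallback against protocol test, t(4 df) scores | 1-3% | 5-12% | 2-6% |

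**3. Effect of ignoring the strata.** Stratified randomization balances the arms within strata, but the unstratified t-test leaves the between-stratum variance in its standard error. If strata explain a share s of the variance, the null rejection rate is about 2 × (1 - Φ(1.96/√(1 - s))).

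- s = 0.15: 1.96/√0.85 = 2.126, giving 0.034 (simulation 3.3%).
- s = 0.05: 1.96/√0.95 = 2.011, giving 0.044 (simulation about 4.5%).

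The departure is towards too few rejections, and it is small when the strata explain little.

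**4. What the baseline score would add.** Let ρ be the baseline-to-end correlation and assume equal SDs. Var(adjusted)/Var(change) = (1 - ρ²)/(2(1 - ρ)) = (1 + ρ)/2.

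| Assumed ρ | Variance ratio | CI width ratio | CI narrower by |
|---|---|---|---|
| 0.3 | 0.65 | 0.806 | 19% |
| 0.5 | 0.75 | 0.866 | 13% |
| 0.7 | 0.85 | 0.922 | 8% |

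If the ratio k of end-of-treatment SD to baseline SD varies from 0.8 to 1.25, the gain over the same correlations runs from 1% to 29%. It is never negative, because the two variances differ by (1 - kρ)² in units of the baseline variance.

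**The case against.** The best defence is that the SAP can be executed as written. Protocol 10 says the SAP details the analyses, and SAP 4.10 fixes one test and one fallback. That stands, so the analyst is not left without an instruction. The protocol nevertheless names a different test itself, and nothing reconciles the two.

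Several stronger readings are tempting, and the documents do not support them:

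- *The sign would hide which device is favoured.* SAP 4.1 summarizes descriptive statistics by treatment, and SAP 4.10 summarizes the changes themselves. With both arms' mean changes shown, arithmetic recovers the arm order, and the baseline and end-of-treatment summaries show the direction of change. Table shells, which SAP 1.2 lists as a related document and which are not available here, may also carry labels.
- *SAP 2.3.2 is a third, conflicting rule.* It gives neither formula nor direction. The supplier instructions are not in the documents, so agreement with either formula cannot be judged. It is a loose cross-reference.
- *TTO change is undefined.* Protocol 9.4 covers it; only the SAP item is missing.
- *Wound strata in Protocol 10.3.2 means the four randomization strata.* It is not defined there. For dressing wear time, SAP 4.11 says wound type where Protocol 10.3.3 says wound strata, so two levels are also possible.
- *The unstratified test inflates false positives.* Any departure is conservative. Two valid tests disagreeing in some trials is expected and does not show bias in either.
- *Leaving out the baseline score is an error.* The change-score comparison is valid in a randomized trial. The cost is precision.

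**Conclusion.** Two contradictions hold on the text alone: the order of subtraction for CWIS and EQ VAS change, and the prespecified test. The first reverses the sign of reported changes, differences and intervals relative to Protocol 9.4; it does not affect two-sided p-values. The second could change a 5% conclusion in a minority of trials, at most about 12% in the settings simulated. That figure rests on assumed strata, distributions and effect sizes. The null rejection rate of about 3.3% depends on strata explaining an assumed 15% of the variance and moves towards 5% as that share falls.

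The absence of the baseline score is an opportunity for a narrower interval and should not be counted as a fault. The point concerns a secondary endpoint and leaves the primary non-inferiority conclusion unaffected. It should be corrected because the repair is cheap.

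**What to change.** 1. **Direction.** In SAP 4.3 items 23 and 25, and in a new item for the TTO index, set change to end of treatment minus baseline, as in Protocol 9.4. Limit the supplier reference in SAP 2.3.2 to scoring and coding. Label the arm order of every quality-of-life difference and state which sign favours PICO. If PICO - tNPWT is chosen, say explicitly that it is the reverse of the primary model's coding.

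2. **Test.** Name the same analysis in Protocol 10.3.2 and SAP 4.10.
   - *Preferred:* for each CWIS score, EQ VAS and the TTO index, a linear model for the end-of-treatment score with treatment, baseline score and the four randomization strata, reporting the difference and 95% CI. If assumptions fail, use the Wilcoxon test on change stratified by the same four strata, with a Hodges-Lehmann estimate and interval stratified in the same way. The residual checks already described in SAP 4.11 can be reused. Keep the CWIS LOCF sensitivity analysis.
   - *Minimum:* the same stratified change-score test in both documents, with wound strata defined.

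**Cost.** SAP wording, one protocol paragraph and minor programming; no new data or visits. The preferred model has six parameters (intercept, treatment, baseline score, three stratum terms) against two for the t-test, so residual degrees of freedom at n = 128 fall from 126 to 122. The 97.5% t quantile moves from 1.9790 to 1.9796, or 0.03%.

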4.11 Exploratory Variables

Presence of Infection and Clinical signs of infection

A Fishers Exact test will be used to test for a difference in the percentage of subjects with incidence of infection presenting during the 12-week treatment period between treatments using the Full Analysis Set, the corresponding 95% confidence intervals will also be presented.

The presence of infection and clinical signs of infection will be summarized by regular Study Visit, at treatment discontinuation and, where appropriate at the one-week confirmation visit. Whether the reference wound is clinically infected at any post baseline assessment will also be summarised.

In addition, the summaries will be separated by reference wound filler used at baseline (gauze, foam or none).

Whether the reference wound has signs of clinical infection at any post baseline assessment and whether the reference wound has signs of clinical infection at treatment discontinuation will be cross tabulated against whether the reference wound has signs of clinical infection at baseline separately for each treatment.

Need for administration of antibiotics and additional interventions

A Fishers Exact test will be used to test for a difference in the percentage of subjects requiring either the administration of antibiotics or additional interventions, between treatments using the Full Analysis Set. The corresponding 95% confidence intervals will also be presented. Individually, Fishers Exact tests will be used to test for a difference in the percentage of subjects requiring the administration of antibiotics and additional interventions separately, between treatments.

The need for administration of antibiotics and additional interventions (and either intervention), and type of intervention will be summarized at per subject by treatment and wound type.

Dressing wear time

A linear regression model will be fitted to the average wear time per subject. Treatment, center, wound type, baseline ulcer area, baseline exudate level and baseline mobility level will be included in the initial model. The difference between the two treatments in terms of average wear time per subject (treatment parameter estimate) will be presented along with the 95% confidence intervals.

The standardised residuals will be assessed for normality (histograms, quantile-quantile plots), homoscedacity (plots against regressors) and no large outliers (magnitude, covariance ratio, DFBETAS). Should these assumptions not hold or if N<20 then non-parametric bootstrapping may be applied to generate 95% confidence intervals of the model estimates. If these differ widely from those of the linear regression model then the bootstrapping estimates will be used these will be used.

The average wear time per subject (at a subject level) will be summarized by treatment, wound type, and the remaining covariates detailed in the previous paragraph. The duration of dressing wear (at a dressing level) will also be summarized by treatment, center, wound type, level of mobility at baseline, level of exudate at the previous assessment and ulcer area (categorized) at the previous assessment.

ST:

9 7 5

Reference:

CE/052/PIC

Customer Code:

0 5

Impact of the device on aspects of daily living and satisfaction with device therapy

All response questions to the exit survey will be summarized by treatment, center, wound type and baseline level of mobility.

A Cochran-Mantel-Haenszel will be used to test for a difference between treatments in individual responses to the Exit Survey for: Overall satisfaction, Opinion of using the device on another wound in future, comfortable to wear, activity level change, and the use of the NPWT device was disruptive to my sleep.

Pain on removal of dressing, at initiation of therapy and during wear

The level of pain on initiation of therapy will be summarized by Study Visit and treatment, separately for each wound type and overall.

The level of pain on initiation of therapy will also be summarized for the ActiV.A.C.® treatment arm overall Study Visits by whether intermittent or continuous therapy is applied, and by pressure range applied (for intermittent – the high therapy pressure value will be used), and compression rate, at the current Study Visit.

The level of pain during wear, and on removal, will be summarized by Study Visit and treatment, separately for each wound type and overall.

The level of pain during wear, and on removal, will also be summarized for the ActiV.A.C.® treatment arm overall Study Visits by whether intermittent or continuous therapy is applied, and by pressure range applied (for intermittent – the high therapy pressure value will be used), and compression rate, at the current Study Visit.

In addition, the level of pain recorded on removal of the screening dressings at Run-In Visit 2 will be summarized by wound type.

Wound Assessment

The presence of necrotic tissue, extent of undermining, the necrotic tissue type and amount, granulation tissue type, epithelialisation tissue type, skin condition surrounding target ulcer, and condition of target ulcer peri-wound will be summarized by Study Visit, at treatment discontinuation and at one-week closure confirmation.

The level (amount) of exudate and the type of exudate will be summarized by Study Visit, at treatment discontinuation and at one-week closure confirmation.

Document Number: 1004313
Document Version: 06

Document Part: 000
Document Status: Released

The total wound status score will be summarized by Study Visit, at treatment discontinuation and at one-week closure confirmation.

